6.10.1. Permitted Medications and Non-Drug Therapies

The following relevant medications are permitted during this study:

- Study-provided albuterol/salbutamol for use as relief medication throughout the run-in and treatment periods
- Short-acting inhaled muscarinic antagonists during washout period only, provided they are washed out for \geq 4 hours prior to Visit 5
- Mucolytics such as acetylcysteine
- Medications for rhinitis (e.g. intranasal corticosteroids, antihistamines, cromolyn, nedocromil, nasal decongestants)
- Influenza vaccine
- Pneumonia vaccine
- Antibiotics for short term treatment (≤14 days) of acute infections including COPD exacerbations

- Systemic corticosteroids for short term (≤14 consecutive days) treatment of COPD exacerbations
- As-needed oxygen use (i.e. ≤ 12 hours per day)
- Pulmonary rehabilitation program in maintenance phase
- Smoking cessation treatment, including a stable regimen of nicotine replacement
- Use of positive airway pressure for sleep apnea
- Localized corticosteroid injections (e.g., intra-articular and epidural)
- Oral muscarinic antagonists for the treatment of overactive bladder are permitted but should be used with caution as they may exacerbate medical conditions that are contraindicated for anticholinergics (e.g., narrow angle glaucoma and bladder outflow obstruction)
- Immunotherapy injections
- Topical or ophthalmic corticosteroids

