6.1.2. Medical Conditions and Concomitant Medications

The number and percentage of subjects reporting each current medical condition will be presented for the overall population. This table will include a category of 'Any Cardiovascular Risk Factor' and will present all medical conditions regardless of frequency. The table will be repeated for past medical conditions.

Non-COPD medications will be summarised by Anatomical-Therapeutic-Chemical (ATC) level 1 and ingredient. Multi-ingredient medications will be presented according to their combination ATC classification rather than the classifications of the ingredients.

Respiratory Medication Class (RMC) will be provided by Data Management for each COPD concomitant medication. COPD medications not given for an exacerbation, and medications given for an exacerbation, will be summarised by Respiratory Medication Class (RMC).

COPD and non-COPD medications will be listed separately. The COPD medications listing will indicate whether each medication was taken for an exacerbation. Both listings will indicate in which treatment state each medication was taken (Pre-Run-in, During Run-in, On-treatment, During Washout, Post-treatment).

A listing of the relationship between ATC Level 1, ingredient and verbatim text will be produced for non-COPD medications only.

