10.4.1.1. Treatment States for Concomitant Medication Data

The following rules will be used to classify a concomitant medication as being taken during one or more study treatment phases (pre-treatment, on-treatment and post-treatment):

DATE RULES	PRETRT	DURTRT	POSTTRT
	(Pre treatment)	(On treatment)	(Post treatment)
mststdt = .	Y		
mststdt ^=.	Y		
AND			
(cmstdt < mststdt OR cmprior = Y)			
AND			
cmenal <= msisiai	V	V	
	ř	ř	
(cmstdt < mststdt OR cmprior = Y)			
AND			
mststdt < cmendt <= mstendt			
mststdt ^=.	Y	Y	Y
AND			
(cmstdt < mststdt OR cmprior = Y)			
AND			
(cmenat > mstenat OR cmongo = Y)		N/	
		Y	
AND metetdt <= cmetdt <= metendt			
AND			
mststdt <= cmendt <= mstendt			
mststdt ^= .		Y	Y
AND			
mststdt <= cmstdt <= mstendt			
AND			
(cmendt > mstendt OR cmongo = Y)			
mststdt ^= .			Y
AND			
cmstat>-mstenat	1	1	

cmstdt=start date of the concomitant medication, cmendt=end date of the concomitant medication, mststdt =start date of the study medication, mstendt =end date of the study medication

The following SAS code will be used:

```
if mststdt=. then do;
 pretrt="Y"; durtrt="; posttrt=";
end;
if mststdt ne . and (cmstdt2 < mststdt or cmprior='Y') and (cmendt2 <= mststdt) then do;
 pretrt='Y'; durtrt="; posttrt=";
end:
if mststdt ne . and (cmstdt2 < mststdt or cmprior='Y') and mststdt < cmendt2 <= mstendt then do;
 pretrt='Y'; durtrt='Y'; posttrt='';
end:
if mststdt ne . and (cmstdt2 < mststdt or cmprior='Y') and (cmendt2 > mstendt or cmongo='Y') then do;
 pretrt='Y'; durtrt='Y'; posttrt='Y';
end
if mststdt ne . and mststdt <= cmstdt2 <= mstendt and mststdt <= cmendt2 <= mstendt then do;
 pretrt="; durtrt='Y'; posttrt=";
end:
if mststdt ne . and mststdt <= cmstdt2 <= mstendt and (cmendt2 > mstendt or cmongo='Y') then do;
 pretrt="; durtrt='Y'; posttrt='Y';
end;
if mststdt ne . and cmstdt2 >= mstendt then do;
 pretrt="; durtrt="; posttrt='Y';
end;
```

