10.4.1.3. Treatment States for COPD Exacerbation Data

Classification of a COPD exacerbation as having onset on- or post-treatment will be made with reference to the study treatment start and stop dates and the exacerbation onset date. If the exacerbation onset date is missing or partial then the exacerbation will be considered on-treatment unless there is evidence to the contrary (e.g. the month of the onset date is present and is less than the month of the first dose of study medication). Exacerbations with onset on the day after the last day of a treatment will be considered on-treatment. Other exacerbations with onset during a washout or follow-up period, or following IP discontinuation will be considered post-treatment but will be assigned to the treatment received in the previous period. Exacerbations which are not considered on- or post-treatment or which are reported by subjects who did not receive treatment will be included in listings only. The duration of the exacerbation will be calculated as (exacerbation resolution date or date of death - exacerbation onset date + 1).

Treatment State	Definition
On-Treatment	If onset date is on or after treatment start date & on or before treatment stop date. Study Treatment Start Date \leq Start Date \leq Study Treatment Stop Date + 1 day
Post-Treatment	If AE onset date is after the treatment stop date. Start Date > Study Treatment Stop Date +1 day

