10.6.4. Efficacy

Sp	Spirometry		
Tro	bugh		
•	The trough value for FEV ₁ , FVC and IC at each of Week 4 and Week 8 is calculated from the values at the assessments made 23 h and 24 h after dosing on the previous day.		
•	If the actual time of an assessment is after the time of dosing on the current day, the value will not be used in the calculation of trough for the PP population.		
•	For the PP population, a value will additionally be excluded from the trough FEV ₁ calculation if the assessment is outside the time window of 22.0-25.0 h after dosing on the previous day.		
•	If one of the values is missing or excluded then the trough will be the single remaining value; otherwise the trough will be the mean of the two values.		
Pre	oportion of responders according to FEV ₁		
•	A subject will be a considered a responder according to trough FEV ₁ if their trough FEV ₁ value		

- has increased by at least 100mL from baseline.
 A subject will be considered a non-responder if their trough FEV₁ value has decreased, has not changed, or has increased by less than 100mL compared to baseline.
- Missing data will be handled as detailed in Section 10.7.2

Calculation of Daily eDiary endpoints

General

Subjects were instructed to complete the daily eDiary in the evening (typically at bedtime). The parameters collected include rescue use and EXACT-PRO scores.

• The tables below show which daily eDiary records are used to calculate the daily eDiary parameters for each period. Any diary data collected in the post-treatment phase of the study will not be slotted. See Section 10.4.1.1 for details on the assignment of treatment phases.

To be used for rescue medication:

Calculation of Daily eDiary endpoints		
Period	First day	Last day
Period 1 Baseline	Latest of (7 days before Visit 2 (Day 1) and day of Visit 1 (Screening))	Day before Visit 2 (Day 1)
Period 1 Week 1-2	Period study day 1 (day of Visit 2)	Period study day 14
Period 1 Week 3-4	Period study day 15	Period study day 28
Period 1 Week 5-6	Period study day 29	Period study day 42
Period 1 Week 7-8	Period study day 43	Earliest of (Period study day 55 and day before Visit 4)
Period 1 Week 1-8	Period study day 1 (day of Visit 2)	Earliest of (Period study day 55 and day before Visit 4)
Period 2 Baseline	Latest of (7 days before Visit 5 (Day 1) and day of Visit 4)	Day before Visit 5 (Day 1)
Period 2 Week 1-2	Period study day 1 (day of Visit 5)	Period study day 14
Period 2 Week 3-4	Period study day 15	Period study day 28

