1.24.	ITT	SP_T13	Summary of COPD Exacerbation History at Screening		SAC	
1.25.	ITT	IDSL-SU1	Summary of Smoking History at Screening	Using Years Smoked, Cigarettes/Day and Smoking Pack Years	SAC	

Study Population Tables						
No.	Population	IDSL / TST ID / Example Shell	Title	Programming Notes	Deliver-able	
1.26.	ITT	SP_T14	Summary of Smoking Status at Screening		SAC	
1.27.	ІТТ	SP_T15	Summary of COPD Concomitant Medications Not Given for a COPD Exacerbation Taken Before Run-in		SAC	
1.28.	ІТТ	SP_T15	Summary of COPD Concomitant Medications Not Given for a COPD Exacerbation Taken During Run-in or Washout	Display treatments instead of total	SAC	
1.29.	ІТТ	SP_T15	Summary of COPD Concomitant Medications Not Given for a COPD Exacerbation Taken On-treatment	Display treatments instead of total	SAC	
1.30.	ІТТ	SP_T15	Summary of COPD Concomitant Medications Not Given for a COPD Exacerbation Taken Post-treatment			
1.31.	ІТТ	SP_T15	Summary of Concomitant Medications Given for a COPD Exacerbation Taken On-treatment	Display treatments instead of total	SAC	
1.32.	ІТТ	SP_T15	Summary of Concomitant Medications Given for a COPD Exacerbation Taken During Washout	Display treatments instead of total		
1.33.	ІТТ	SP_T15	Summary of Concomitant Medications Given for a COPD Exacerbation Taken Post-treatment			
1.34.	ІТТ	IDSL – CM1	Summary of Non-COPD Concomitant Medications Taken On-treatment	Display ATC and ingredient by treatments	SAC	
1.35.	ІТТ	IDSL – CM1	Summary of Non-COPD Concomitant Medications Taken Post-treatment	Display ATC and ingredient by total	SAC	
Baseline Sev	verity					
1.36.	ITT		Summary of Screening Lung Function Test Results		SAC	
1.37.	ITT		Summary of GOLD Grade 1-4, GOLD mMRC Category A- D, GOLD CAT Category A-D and Reversibility at Screening		SAC	
1.38.	ITT		Summary of Screening IC Results		SAC	

Study Population Tables							
No.	No. Population IDSL / TST ID / Example Shell		Title	Programming Notes	Deliver-able		
1.39.	ITT		Summary of mMRC Dyspnoea Scale at Screening		SAC		
Treatment							
1.40.	ITT		Summary of Overall Percentage Treatment Compliance		SAC		

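### The concomitant-medication rule in SAP 10.4.1.1 has no run-in or washout state and no treatment assignment, and it misfiles drugs started on the stop date, so it cannot produce the medication tables the SAP plans

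*SAP*

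**What the plan says.** SAP 10.4.1.1 sets out date rules, followed by SAS code that it says will be used, to "classify a concomitant medication as being taken during one or more study treatment phases (pre-treatment, on-treatment and post-treatment". The only study-treatment dates are defined as "mststdt =start date of the study medication, mstendt =end date of the study medication". There is no period index, no visit date, and no step that links a medication to a treatment.

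Other parts of the SAP ask for more:

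- SAP 6.1.2: "Both listings will indicate in which treatment state each medication was taken (Pre-Run-in, During Run-in, On-treatment, During Washout, Post-treatment". That is five states.
- SAP 10.13.4, Table 1.32: "Summary of Concomitant Medications Given for a COPD Exacerbation Taken During Washout". Table 1.28 covers non-exacerbation COPD drugs taken in run-in or washout.
- The programming notes for Tables 1.28, 1.29, 1.31 and 1.32 call for treatment columns in place of a total.

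The neighbouring rules are fuller. SAP 10.4.1.2 classifies adverse events against the dates of each period. SAP 10.4.1.2 and 10.4.1.3 both assign washout onsets to the treatment of the preceding period and extend on-treatment by one day: "Exacerbations with onset on the day after the last day of a treatment will be considered on-treatment".

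Washout use of recorded drugs is expected. Protocol 6.10.1 permits "Short-acting inhaled muscarinic antagonists during washout period only", and it also permits short courses of systemic corticosteroids and antibiotics for exacerbations.

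**The concern.** In a two-period crossover, three states cut from one pair of dates cannot separate two treatment periods from the washout between them. Tables 1.28, 1.29, 1.31 and 1.32 are where a reader checks whether background, relief and exacerbation drugs were balanced between the two products. If the code is used as written, an anticholinergic permitted only in washout could appear as on-treatment use, where Protocol 6.10.2 prohibits it. A corticosteroid or antibiotic started on the last dosing day could be absent from Table 1.31 while its exacerbation is counted in Table 3.21. The washout table could not be filled from the stated rule at all.

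**Working it through.** The plan gives no figure to reproduce here. The check is to run the seven printed IF steps, in order, on example records.

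**Inputs.** Protocol 4.2 and 7.1 give two 8-week periods, a washout of 21 ± 3 days, and no dosing at Visits 4 and 7. The nominal timeline below is an assumption built on these: Period 1 dosing on days 1–55, washout on days 56–76, Period 2 dosing on days 77–131. Because 10.4.1.1 does not say which dates it means, both readings were run: study-wide (1–131), and per period (1–55 and 77–131).

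| Record (days) | Study-wide dates | Period 1 dates | Period 2 dates | State needed |
|---|---|---|---|---|
| Run-in drug, −10 to −3 | Pre | Pre | Pre | Run-in |
| Period 1 corticosteroid, 20–27 | On | On | Pre | On, Period 1 |
| Washout anticholinergic, 58–75 | On | Post | Pre | Washout |
| Washout corticosteroid, 60–69 | On | Post | Pre | Washout |
| Period 2 corticosteroid, 95–102 | On | Post | On | On, Period 2 |
| Course starting on last dosing day, 131–138 | Post | Post | Post | On (continuing after) |

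**Washout.** No reading returns a washout state. With study-wide dates the off-drug days counted as on-treatment are 77 − 55 − 1 = 21, and 21/131 = 16% of the window. Period 1 and Period 2 drugs also carry the same flag, with nothing to tell the treatments apart.

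**Run-in.** A run-in drug and a pre-run-in drug both come out as pre-treatment, so Tables 1.27 and 1.28 cannot be separated from the flags.

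**Stop date.** The on-treatment steps accept a start date up to and including mstendt. The last step, "if mststdt ne . and cmstdt2 >= mstendt then do", is also true at equality; it runs last and resets the record to post-treatment only. With study-wide dates this affects starts on day 131. With period dates it also affects day 55. A start on the following day is post-treatment for that stop date as well. SAP 10.4.1.3 calls an exacerbation with onset on either day on-treatment, so the event and its treatment can be filed differently.

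**Check on a partial repair.** If only the last condition is changed, to a start later than mstendt + 1, the on-treatment steps still stop at mstendt. A drug starting on mstendt + 1 then gets no state: days 56–60 against stop day 55, and days 132–138 against stop day 131. When the on-treatment upper bound is also moved to mstendt + 1, both records return on-treatment and post-treatment flags, as they should for courses that begin on that day and continue.

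**The case against.** The strongest defence is that the dates may be meant per period, as they are in 10.4.1.2 and in the exposure rules of 10.6.3, and that washout can then be recovered. This has force. Over all 24,310 whole-day start and end pairs from day −60 to day 159 on the timeline above, the combination of post-treatment for Period 1 and pre-treatment for Period 2 identified overlap with washout in every case except a drug taken only on day 55. But that combining step is not in the SAP, it works only for subjects who enter both periods, and it does not repair the stop date, the run-in state or the treatment columns. A programmer could add the missing steps, but by-treatment attribution would then be an undocumented choice.

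It is also fair to say that Tables 1.31 and 3.21 classify by different dates (the drug and the exacerbation onset), so they can differ even with correct code. The overwrite is an avoidable addition to that.

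Two stronger readings are tempting and should not be drawn:

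- *Loss of the Period 2 diary baselines.* SAP 10.6.4 says "Any diary data collected in the post-treatment phase of the study will not be slotted" and refers to 10.4.1.1 for the phases. A reader might infer that washout diary days are dropped. The slotting tables under that sentence, and the baseline definitions in 10.5.2.1, explicitly take the Period 2 rescue and E-RS baselines from the days before Visit 5. The Time and Events table keeps washout separate from post-treatment, which there covers only early withdrawal and follow-up. The specific rule governs.
- *An effect on the primary analysis.* SAP 10.1.1 describes the per-protocol medication review without using these flags, so no effect on exclusions or on trough FEV1 is shown.

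**Conclusion.** The point holds for the medication displays. As printed, 10.4.1.1 cannot supply the run-in and washout states required by SAP 6.1.2 and Tables 1.28 and 1.32, and it gives no treatment for the columns of Tables 1.28, 1.29, 1.31 and 1.32. Drugs started on the stop date are filed wrongly whichever dates are meant. This is more than missing detail, because the SAP states that this code will be used.

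The form of the washout error depends on the reading: on-treatment with study-wide dates, post- and pre-treatment with period dates. The documents do not settle which applies, so it should not be asserted that a single study-wide pair is used.

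The consequence is descriptive only. Study-provided albuterol/salbutamol is untouched, because Protocol 6.10 keeps it out of the eCRF; the washout relief at issue is short-acting anticholinergics. The number of records affected cannot be estimated, since the documents forecast neither washout relief use nor exacerbation treatment. The 16% figure is a share of days on an assumed nominal timeline, not of records.

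**What to change.** Rewrite the rule and code in SAP 10.4.1.1 before database freeze:

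1. Use start and stop dates for each period, and define pre-run-in, run-in, on-treatment (Period 1, Period 2), washout and post-treatment, bounded by visit and dosing dates.
2. Make the states mutually exclusive for a drug's start date. Extend the on-treatment upper bound to mstendt + 1 day, and begin washout (or post-treatment, after Period 2 or withdrawal) at cmstdt > mstendt + 1 day. Both changes are needed together. A drug that continues into a later state may still carry that state's flag.
3. Attribute washout drugs to the treatment of the preceding period, as 10.4.1.2 and 10.4.1.3 do for events. Show run-in drugs in a total column, since no treatment has yet been given, and amend the note on Table 1.28 to match.
4. As a clarification only, state in 10.6.4 that the post-treatment phase means after the Period 2 stop date or after withdrawal.

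The cost is SAP wording and a short derivation program. No new data are needed beyond the visit, dosing and medication dates already collected.

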10.4.1.2. Treatment States for AE Data

Classification of an AE as pre-, on- or post-treatment will be made with reference to the study treatment start and stop dates for each period and the AE onset date. If the AE onset date is missing or partial then the AE will be considered on-treatment unless there is evidence to the contrary (e.g. the month of the onset date is present and is less than the month of the first dose of study treatment). AEs with onset on the day after the last day of treatment will be considered on-treatment. Other AEs with onset during the wash-out or follow-up periods, or following IP discontinuation will be considered post-treatment but will be assigned to the treatment received in the previous period. AEs with missing or partial onset dates which are not classified will be included in listings only. AEs reported by subjects who did not receive treatment will be considered pre-treatment.

Treatment State	Definition
Pre-Treatment	AE Onset Date < First Study Treatment Start Date
On-Treatment	If AE onset date is on or after treatment start date & on or before treatment stop date. Study Treatment Start Date \leq AE Start Date \leq Study Treatment Stop Date + 1 day
Post-Treatment	If AE onset date is after the treatment stop date plus 1 day.
	AE Start Date > Study Treatment Stop Date + 1 day
Onset Time	If Treatment Start Date > AE Onset Date: = AE Onset Date - Treatment Start Date
Since 1 st Dose	If Treatment Start Date ≤ AE Onset Date: = AE Onset Date - Treatment Start Date +1
(Days)	Missing otherwise.
Duration (Days)	AE Resolution Date – AE Onset Date + 1
Drug-related	If relationship is marked 'YES' on [Inform/CRF OR value is missing].

NOTES:

If the study treatment stop date is missing then the AE will be considered to be On-Treatment.

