Any history of allergy or hypersensitivity to any anticholinergic/muscarinic receptor antagonist, sympathomimetic, lactose/milk protein or magnesium stearate.

[8] Antimuscarinic effects:

Subjects with medical conditions such as narrow-angle glaucoma, urinary retention, prostatic hypertrophy, or bladder neck obstruction should be excluded unless, in the opinion of the study physician, the benefit outweighs the risk.

[9] Hospitalization:

Hospitalization for COPD or pneumonia within 12 weeks prior to Visit 1. **Pneumonia** and/or moderate or severe COPD exacerbation that has not resolved at least 14 days prior to Screening (V1) and at least 30 days following the last dose of oral/systemic corticosteroids (if applicable).

Other respiratory tract infections that have not resolved at least 7 days prior to Screening (V1).

[10] Lung Resection:

Subjects with lung volume reduction surgery (including procedures such as endobronchial valves) within the 12 months prior to Screening (V1).

[11] **12-Lead ECG:**

The Investigator will determine the clinical significance of each abnormal ECG finding in relation to the subject's medical history and exclude subjects who would be at undue risk by participating in the trial. Subjects with the following abnormalities are excluded from

participation in the study:

- Atrial fibrillation with rapid ventricular rate >120 bpm
- Sustained or nonsustained ventricular tachycardia
- Second degree heart block Mobitz type II or third degree heart block (unless pacemaker or defibrillator had been inserted)

[12] Medication Prior to Spirometry:

Unable to withhold albuterol/salbutamol for the 4 hour period required prior to spirometry testing at each study visit.

[13] Medications Prior to Screening:

Use of the following medications according to the following defined time intervals prior to Screening (Visit 1):

Medication	Time interval
Depot corticosteroids	12 weeks
Systemic, oral or parenteral corticosteroids1	6 weeks
Antibiotics (for lower respiratory tract infection)	6 weeks
LABA/Inhaled Corticosteroid (ICS) combination products	30 days
ICS	30 days
Phosphodiesterase 4 (PDE ₄) Inhibitor (roflumilast)	14 days
Inhaled long acting beta ₂ agonists (LABAs):	
-salmeterol, formoterol	48 hours
-olodaterol, indacaterol, vilanterol	14 days
Long-acting muscarinic antagonists (LAMAs): tiotropium,	7 days
aclidinium, glycopyrronium, umeclidinium	
LAMA/LABA combination products	Apply whichever mono
	component has the longest
	washout

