7.3. Efficacy

7.3.1. Spirometry

Spirometry measurements will be obtained using spirometry equipment that meets or exceeds the minimal performance recommendations of the ATS [Miller, 2005]. All sites will use standardized spirometry equipment provided by an external vendor.

All subjects will have spirometry performed at Screening and at Visits 2, 3, 4, 5, 6, and 7 during the treatment period. For FEV_1 and FVC determinations, at least 3 acceptable spirometry efforts (with no more than 8) should be obtained. Acceptable spirometry efforts should have a satisfactory start of test and end of test (i.e. a plateau in the volume time curve) and be free from artifacts due to cough, early termination, poor effort, obstructed mouthpiece, equipment malfunction, or other reasons [Miller, 2005].

The largest FEV_1 and FVC from the 3 acceptable efforts should be recorded, even if they do not come from the same effort.

Spirometry for FEV₁, and FVC assessments that is not obtained as follows will be considered a protocol deviation:

- Started between 6:00AM and 11:00AM.
- After withholding albuterol/salbutamol (all visits) ≥4 hours and after withholding short-acting inhaled anticholinergics taken during washout for ≥4 hours prior to Visit 5
- At Visit 1, after withholding COPD medications as specified in the exclusion criteria in Section 5.
- At Visit 3 and 6 after withholding the morning dose of study drug (note study drug will not be administered at visits 4 and 7).
- Pre dose assessments performed prior dosing

Subjects should refrain from smoking for 1 hour prior to each pulmonary function test.

On Day 1 of each treatment period (Visits 2 and 5 respectively), pre-dose spirometry measurements should be conducted 30 minutes and 5 minutes prior to dosing. Trough measurements on Weeks 4 (Visits 3 and 6) and Week 8 (Visits 4 and 7) of each treatment period should be done 23 hours and 24 hours after the previous day's dose of study medication. Any trough FEV₁ measurement collected outside 22.0-25.0 hours after the previous day's dose will be considered protocol deviations with data exclusion from the Per Protocol population analysis of trough FEV₁.

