9.4.2. Safety Analyses

AEs will be coded using the standard GSK dictionary, Medical Dictionary for Regulatory Activities (MedDRA), and grouped by body system. AEs with onset pre-treatment or during active treatment will be summarized separately. The number and percentage of subjects experiencing at least one AE of any type, AEs within each body system and AEs within each preferred term will be presented for each treatment group. Separate summaries will be provided for all AEs, drug related AEs, SAEs and AEs leading to withdrawal.

All SAEs will be tabulated and listed by treatment group. Deaths and SAEs will be documented in case narrative format.

The proportion of subjects experiencing a COPD exacerbation will be tabulated.

Full details of the analyses to be performed on all efficacy and safety endpoints will be given in the RAP.

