10.13.7. Safety Tables

Safety : Tal	oles				
No.	Population	IDSL / TST ID / Example Shell	Title	Programming Notes	Deliver-able
Adverse Ev	vents				
3.1.	ITT	S_T01	Overview of Adverse Events		SAC
3.2.	ITT	S_T02 (AE1)	Summary of On-treatment Adverse Events		SAC
3.3.	ITT	S_T02 (AE1)	Summary of Post-treatment Adverse Events	Include footnote 'Note: AEs with onset during the washout or follow-up period or following IP discontinuation are considered post-treatment and have been assigned to the treatment previously received.'	SAC
3.4.	ITT	S_T02 (AE1)	Summary of On-treatment Adverse Events Reported by 3% (after rounding) or More Subjects in Any Treatment		SAC
3.5.	ITT	S_T02 (AE1)	Summary of the 10 Most Frequent On-treatment Adverse Events in Each Treatment	Count most frequent number of events, not subjects and %. Sort by descending total incidence (sum of number of subjects with event).	SAC
3.6.	ITT	S_T02 (AE1)	Summary of On-treatment Drug Related Adverse Events		SAC
3.7.	ASE	S_T02 (AE1)	Summary of Pre-treatment Fatal Serious Adverse Events		SAC
3.8.	ITT	S_T02 (AE1)	Summary of On-treatment Fatal Serious Adverse Events		SAC
3.9.	ITT	S_T02 (AE1)	Summary of Post-treatment Fatal Serious Adverse Events	Include footnote 'Note: AEs with onset during the washout or follow-up period or following IP	SAC

Safety : Tables								
No.	Population	IDSL / TST ID / Example Shell	Title	Programming Notes	Deliver-able			
				discontinuation are considered post-treatment and have been assigned to the treatment previously received.'				
3.10.	ITT	S_T02 (AE1)	Summary of On-treatment Drug-related Fatal Serious Adverse Events		SAC			
3.11.	ASE	S_T02 (AE1)	Summary of Pre-treatment Non-fatal Serious Adverse Events		SAC			
3.12.	ITT	S_T02 (AE1)	Summary of On-treatment Non-fatal Serious Adverse Events		SAC			
3.13.	ITT	S_T02 (AE1)	Summary of Post-treatment Non-fatal Serious Adverse Events	Include footnote 'Note: AEs with onset during the washout or follow-up period or following IP discontinuation are considered post-treatment and have been assigned to the treatment previously received.'	SAC			
3.14.	ITT	S_T02 (AE1)	Summary of On-treatment Drug-related Non-fatal Serious Adverse Events		SAC			
3.15.	ITT	S_T03	Summary of On-treatment Adverse Events of Special Interest		SAC			
3.16.	ITT	S_T02 (AE1)	Summary of On-treatment Adverse Events Leading to Permanent Discontinuation of Study Treatment or Withdrawal from the Study		SAC			

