3.17.	ASE	S_T02 (AE1)	Summary of Pre-treatment Adverse Events Leading Withdrawal from the Study		SAC			
3.18.	ASE	IDSL -AE2	Relationship between Adverse Event System Organ Class, Preferred Term and Verbatim Text		SAC			

Safety : Tables								
No.	Population	IDSL / TST ID / Example Shell	Title	Programming Notes	Deliver-able			
3.19.	ASE	EMA Table 3	Summary of Non-serious Adverse Events > 3% (before rounding) in any treatment	EMA Reporting Package Macro: EMA_AE	SAC			
3.20.	ASE	Standard EMA output	Summary of On-treatment Adverse Events Categories by Age Subgroup	EMA Reporting Package Macro: EMA_AE	SAC			
COPD exac	erbations	·	·	·	•			
3.21.	ITT	S_T04	Summary of On-treatment COPD Exacerbations		SAC			
3.22.	ITT	S_T04	Summary of Post-treatment COPD Exacerbations	Include footnote 'Note: Exacerbations with onset during the washout or follow- up period or following IP discontinuation are considered post-treatment and have been assigned to the treatment previously received.'	SAC			
Extent of Ex	xposure							
3.23.	ITT	S_T05	Summary of Exposure		SAC			

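### An adverse event that starts in washout and keeps a subject out of Period 2 is in no by-treatment table of AEs leading to withdrawal, and post-treatment AEs are missing from the drug-related and special-interest tables

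*SAP*

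**What the plan says.** SAP 10.4.1.2 gives each AE one of three states.

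- **Pre-treatment:** "AE Onset Date < First Study Treatment Start Date".
- **On-treatment:** from the start of treatment in a period to its stop date plus one day. The text says that "AEs with onset on the day after the last day of treatment will be considered on-treatment".
- **Post-treatment:** "Other AEs with onset during the wash-out or follow-up periods, or following IP discontinuation will be considered post-treatment". These events are assigned to the treatment of the previous period.

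The safety tables in SAP 10.13.7 use these states. Post-treatment AEs have three tables: all AEs (3.3), fatal SAEs (3.9) and non-fatal SAEs (3.13). The drug-related tables (3.6, 3.10, 3.14) and the special-interest table (3.15) are titled on-treatment. Withdrawal has two tables. Table 3.16 is the "Summary of On-treatment Adverse Events Leading to Permanent Discontinuation of Study Treatment or Withdrawal from the Study". Table 3.17 is the "Summary of Pre-treatment Adverse Events Leading Withdrawal from the Study". Table 6 in SAP 8.2.1 has the same pattern.

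Protocol 9.4.2 commits to this: "Separate summaries will be provided for all AEs, drug related AEs, SAEs and AEs leading to withdrawal". SAP Table 1, which records changes from the protocol analysis, has no entry limiting any of these summaries to on-treatment events.

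**The concern.** The plan credits a washout AE to the drug just stopped, then leaves it out of that drug's counts of related events, special-interest events and events leading to withdrawal. The withdrawal table matters most. In a two-period crossover, washout is a natural point for a subject to leave, and an AE starting then can be the reason. Neither withdrawal table can hold it.

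Safety and tolerability of the two drugs is a stated objective, and these tables are where a reader would look for it. The SAP handles neighbouring cases more fully. It has a withdrawal table for the time before first treatment, although Protocol 7.5.2.1 collects AEs in general only from the start of treatment. For COPD exacerbations, SAP 8.2.3 reports subjects withdrawn separately for on-treatment and post-treatment onset. AEs have no such parallel.

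**Working it through.** **Step 1: trace one event.** Take an invented case. A subject's last Period 1 dose is on day 55. A special-interest AE starts on day 63, the investigator calls it related, and the subject withdraws before Visit 5. Day 63 is after first treatment, so the AE is not pre-treatment. It is later than day 55 + 1 = 56, so it is not on-treatment. It is post-treatment and assigned to the Period 1 drug.

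| Display | State covered | Holds this AE? |
|---|---|---|
| Table 3.3, all AEs | Post-treatment | Yes |
| Tables 3.9, 3.13, SAEs | Post-treatment | Only if serious |
| Tables 3.6, 3.10, 3.14, drug-related | On-treatment | No |
| Table 3.15, special interest | On-treatment | No |
| Table 3.16, leading to discontinuation or withdrawal | On-treatment | No |
| Table 3.17, leading to withdrawal | Before first treatment | No |
| Listings 11 and 14 | Any | Yes, case by case |
| Withdrawal reasons by period (SAP 6.1.1) | Includes washout | Counted by reason, not by AE term |

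Two other displays do not clearly close the gap. SAP Table 6 names an SAE summary by preferred term with drug-related status and no on-treatment limit, but Appendix 13 has no entry for it, and it would cover serious events only. Table 3.1, the AE overview, is limited to on-treatment events in SAP Table 6 but not in Appendix 13, and its shell is not in the documents.

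**Step 2: time affected.** The plan's stated total of about 22 weeks reproduces: 2 + 8 + 3 + 8 + 1 = 22. From first dose to follow-up contact it is 8 + 3 + 8 + 1 = 20 weeks, or 140 days.

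The visit days come from the Time and Events Table (Protocol 7.1), for a completer on the nominal schedule:

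- Visit 2 is day 1 and Visit 4 is day 56. Protocol 7.3.1 says "note study drug will not be administered at visits 4 and 7", so the last Period 1 dose is taken to be on day 55 and the on-treatment window ends on day 56.
- Visit 5 is 56 + 21 = day 77. Post-treatment washout days are 57 to 76, which is 20 days.
- Visit 7 is 77 + 56 = day 133, the last on-treatment day of Period 2. The contact is 133 + 7 = day 140. Days 134 to 140 add 7.
- Post-treatment share: (20 + 7)/140 = 27/140 = 19%. Washout alone: 20/140 = 14%.

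Across the windows for washout (21 ± 3 days) and follow-up (7 ± 3 days):

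- 18-day washout, 4-day follow-up: (17 + 4)/134 = 21/134 = 16%.
- 24-day washout, 10-day follow-up: (23 + 10)/146 = 33/146 = 23%.

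The result depends little on how days are counted. Taking one day off each of the 21 and 7 gives 26/140 = 18.6%.

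**Step 3: events affected.** This cannot be computed. The documents give no AE rate and no rate of withdrawal in washout.

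**The case against.** The strongest reply is that nothing is lost. The stated safety endpoints are the incidence of AEs and of COPD exacerbations, and both are tabulated after treatment by preceding drug (Tables 3.3 and 3.22). Special-interest terms that start in washout are in Table 3.3, though not grouped. Listing 14 shows every AE that led to withdrawal. The restricted tables are labelled on-treatment, so they do not mislead. Protocol 9.4.2 itself speaks only of onset before treatment or during active treatment, so the SAP goes beyond that framework by adding post-treatment tables. All of this stands, and it makes this a reporting gap, not lost data or a clear breach of protocol. It does not supply the missing table: a case listing is not a by-treatment summary by AE term.

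A reader might also infer from the protocol's washout figures that drug effects on safety persist through these days. Protocol 5.2 sets 14 days before screening for "olodaterol, indacaterol, vilanterol" and 7 days for LAMAs, and Protocol 4.4 justifies 3 weeks between periods. The documents do not support that inference. The first two are limits on medication before screening, and the third is argued from lung function. None is a risk window for AEs. Events in washout may also reflect being off maintenance therapy, which is a good reason to keep them apart from on-treatment counts.

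Nor is 19% of days 19% of events. Follow-up days cannot lead to withdrawal before completion, since completion is at Visit 7 (Protocol 5.7).

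**Conclusion.** The gap is real and narrow. An AE with onset more than one day after the last dose of a period is in no drug-related, special-interest or AE-withdrawal table, although the SAP assigns it to a drug. The main consequence is that an AE starting in washout that stops a subject entering Period 2 is in no by-treatment table of AEs leading to withdrawal.

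The limits are these. AEs that start on treatment or on the day after the last dose stay in Table 3.16, even if the subject withdraws later. Missing or partial onset dates default to on-treatment unless there is evidence otherwise. Non-serious COPD exacerbations are not AEs here and are covered by Table 3.22.

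About 27 of 140 nominal days are affected (16-23% across windows), and about 20 of them fall before Period 2. This assumes a completer whose last dose is the day before Visit 4 and Visit 7. The number of events is unknown and may be small. It would be too strong to say that the AE-withdrawal and disposition tables will disagree. They differ on this account only if such an event occurs, and disposition counts one primary reason per subject while Table 3.16 counts AEs. The change is worth making because it completes the per-drug tolerability picture. Efficacy conclusions are not affected.

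**What to change.** In SAP 8.2.1 and 10.13.7:

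1. Extend Table 3.16 to post-treatment AEs, by preceding treatment, and do the same for Tables 3.6 and 3.15. Use separate post-treatment tables or columns labelled by treatment state, and do not merge them with on-treatment counts. Reuse the Table 3.3 footnote on assignment to the previous treatment.
2. Reconcile the AE-withdrawal counts with the disposition summary for Period 1, washout and Period 2, and explain any difference.
3. Reconcile SAP Table 6 with Appendix 13 for the SAE summary by drug-related status: add the missing entry and state which treatment states it covers, or remove it from Table 6.

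The cost is about three tables or column sets built from existing data and flags. The downside is more output and possibly slightly less favourable counts for each drug.
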